|  | 3. Simultaneous Kidney and Pancreas
Transplant (SPK)  |
| Investigational medicinal product and dosage             | N/A; this is not a trial of an investigational medical product   |
| Active comparator product(s)                             | N/A  |
| Route(s) of administration                               | N/A  |
| Maximum duration of treatment of a subject               | N/A  |
| Procedures: Screening & enrolment                        | All patients undergoing kidney
transplantation will be considered for
enrolment  |
| Baseline   | Baseline recipient data will be recorded.  |
| Treatment period
End of Study                         | The intervention is non-pharmacological.
Patients will be randomised to one of two
groups: control (conventional cystoscopic
TUS removal) or trial (new method with early
TUS removal), refer to flow diagram. Trial
group will have their TUS attached to their
catheter during surgery. Both Catheter and
TUS will be removed on day 5 post surgery.
The control arm will undergo catheter
removal on day 5 and the current
conventional method of cystoscopic TUS
removal at week 6.
Follow-up visits and tests are part of the
transplantation protocol in the centres. Data
will be obtained from the medical notes and
local centre databases for up to 1 year
Patients will be followed-up for 1 year |
| Procedures for safety monitoring                         | Complications will be reported to the Data   |
| during trial   | Safety Monitoring Committee (DMC). The   |
|  | committee will meet in the $1^{st}$ month & then at 3 monthly intervals.   |
| Criteria for withdrawal of patients on
safety grounds | 
 
An increased rate of stent related
complications in the eTUSr arm (>20%)
 
An increase in ureteric complications in
the eTUSr arm (>1% urinary leak or >2
cases in the 1st month; 20% ureteric
stenosis or >3 cases at 3 months)
 
Clinically and statistically different
outcomes are shown in either arm and
continuation of the study is considered
unethical
 
  |
| Regulatory submissions on safety grounds                 | Not required as not a CTIMP  |

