#### **Secondary Endpoints**

- 1) Incidence of ureteric leak at 3months post transplantation for each arm
- 2) Incidence of ureteric stenosis at 6 months post transplantation for each arm
- 3) Quality of life assessment using FAIT-U and EQ-5D at week 1 and week 6 post transplant
- 4) Patient completed diary cards (day of stent removal)
- 5) NHS reference costs for stent removal procedure and management of stent related complications at 6 months.

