# 7.1 TUS-related complication definitions:

Complications are defined as occurring in first 3 months post transplant except transplant ureteric stenosis which can develop insidiously and so will be recorded for the first 6 months post transplant.

- Urinary Tract Infection (UTI) microbiology (MC&S) in the early (<3month) post transplant setting
  - Symptomatic dysuria / fever / pain over transplant or native kidneys with Mid Stream Urine (MSU) culture bacteria  $> 10^{x^2}$  with pyuria
  - Asymptomatic Mid Stream Urine (MSU) culture bacteria  $> 10^{x5}$  with pyuria
- Stent migration ultrasound and / or plain x-ray diagnosis of TUS not appropriately positioned (coils not in both the transplant renal pelvis and the bladder).
- Stent pain requiring stent removal
- Haematuria frank haematuria requiring catheterisation +/- irrigation
- Stent Fragmentation

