#### 8.2 Potential risks

There is the potential for unexpected complications in the new technique arm of the study. These may be related to the early removal of the stent on the 5th post operative day.

- The main potential complication is an increase in the urinary leak rate (>1%). This would be clinically detectable by a decrease in voided urine volume and discomfort around the transplanted kidney. Investigation would be with an ultrasound scan. Treatment would be with replacement of the urinary catheter for 2 weeks and a cystogram before removal. Any incident of urinary leak in either group would be immediately reported to the Trial Data Safety Monitoring Committee. An increase incidence in urinary leak rates (>2 cases in the first month) in either arm would trigger a trial safety review and if necessary temporary cessation in the study until appropriate clinical review. However, data to date from the literature  and personal communications (The Mayo Clinic, 2006) suggest no increase in urinary leak complication rate with the new technique.
- There is the potential that we find an increase rate (>15-20%) of ureteric stenosis in the early (3 month) post transplant period. This would present with a decrease in void volume, discomfort around the transplant or deteriorating renal function.

Investigation would involve an ultrasound scan and be initially managed with either nephrostomy or retrograde insertion of ureteric stent. Nephrostogram / retrograde x-ray would be obtained to confirm diagnosis. Treatment would involve either endo-urological or an open corrective surgical approach. >3 cases of stenosis in the first 3 months would generate trial review. Data to date does not suggest increased complications of stenosis with early removal of ureteric stents.

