# 8.4 Data Monitoring Committee

There will be not be a separate Trial Steering Committee, but the Trial will be overseen by the Data Monitoring Committee below.

*Committee Chair:* [name] (Consultant in Nephrology, GSTT) *Members:* [name] (Consultant in Renal Transplantation, GSTT and coapplicant) [name] (Consultant in Urology, GSTT); [name] (Head of Clinical Governance GSTT Renal Department); [name] (Consultant in Renal Transplantation GSTT and lead applicant); [name] (Consultant Paediatric Nephrologist, Evelina Children's Hospital, GSTT); [name] (Professor of Medical Statistics, King's College London), [name] (Research Fellow in Biostatistics and Bioinformatics, MRC centre for transplantation); [name] (Clinical Research Fellow in Urology, GSTT). The committee will assess trial progress, occurrence of adverse events and other aspects of the trial such as recruitment. The committee will meet in the 1st month & then at 3 monthly intervals.

The trial will be stopped if in the opinion of the Data Monitoring Committee the following conditions have been satisfied:

An increase rate of stent related complications in the eTUSr arm (>20%) An increase in ureteric complications in the eTUSr arm (>1% urinary leak or >2 cases in the 1st month; 20% ureteric stenosis or >3 cases at 3 months) Clinically and statistically different outcomes are shown in either arm and continuation of the study is considered unethical.

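### No pre-specified case count for ureteric stenosis covers months 4 to 6 after transplant, although the protocol follows stenosis to 6 months because it develops insidiously

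*Protocol*

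**What the plan says.** Three places in the protocol set a numerical safety limit for stenosis.

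- Section 8.4 (Data Monitoring Committee), as a condition for stopping the trial on the early-removal (eTUSr) arm: "20% ureteric stenosis or >3 cases at 3 months". The synopsis has the same limit under its safety criteria.
- Section 8.2 (Potential risks), as a trigger for review: ">3 cases of stenosis in the first 3 months would generate trial review". The same bullet describes the risk as an "increase rate (>15-20%) of ureteric stenosis in the early (3 month) post transplant period".

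The follow-up of stenosis is longer. Section 7.1 gives most complications a 3-month window but makes an exception for "transplant ureteric stenosis which can develop insidiously and so will be recorded for the first 6 months post transplant". The secondary endpoint in section 5.8 is "Incidence of ureteric stenosis at 6 months post transplantation for each arm". The synopsis adds: "Patients will be followed-up for 1 year".

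Section 8.4 has one further stopping condition without a time window: "Clinically and statistically different outcomes are shown in either arm and continuation of the study is considered unethical". It also asks the committee to look at adverse events in general, meeting in the first month and then every 3 months.

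**The concern.** The protocol judges 3 months too short a period in which to record stenosis, and then uses 3 months for the case count that guards against it. Stenosis is one of the two ureteric harms that section 8.2 names for early stent removal. If the 3 months run from each transplant, cases in months 4 to 6 add to no count. If they run from the start of the trial, the count lapses early in a recruitment period that section 9 puts at 2 years. On either reading, late stenoses could build up in the eTUSr arm while recruitment continues without reaching the count, and any response would rest on the committee's judgement alone.

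**Working it through.** **1. The denominator.** Section 5.5 gives 88 per group (20% against 5%) and 160 per group (15% against 5%), with two-sided 5% error and 80% power. The two-proportion formula with continuity correction returns exactly 88 and 160 (76 and 141 without it). The eTUSr arm is therefore taken as 88, with 160 as the alternative.

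**2. Which limb does the work.** More than 3 cases means at least 4.

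| eTUSr arm | Count limit | 20% limit |
|---|---|---|
| 88 | 4 cases (4/88 = 4.5%) | 0.20 × 88 = 17.6, so 18 cases |
| 160 | 4 cases (4/160 = 2.5%) | 0.20 × 160 = 32 cases |

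At full enrolment the count is met long before the percentage, so the window on the count decides how sensitive the safeguard is.

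**3. Effect of the window, complete follow-up.** The protocol states no operating characteristic for this trigger and no stenosis rate, so there is no figure of its own to reproduce. Let q be the assumed six-month stenosis risk and f the assumed share of cases diagnosed by month 3. The chance of reaching the count is P(X ≥ 4), with X ~ Binomial(n, q × f) for the 3-month count and X ~ Binomial(n, q) for the 6-month count.

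| n | q | 3 months, f = 0.25 | f = 0.50 | f = 0.75 | 6 months |
|---|---|---|---|---|---|
| 88 | 2% | 0.001 | 0.012 | 0.044 | 0.100 |
| 88 | 3% | 0.004 | 0.044 | 0.137 | 0.271 |
| 88 | 5% | 0.025 | 0.179 | 0.421 | 0.647 |
| 88 | 8% | 0.100 | 0.470 | 0.781 | 0.929 |
| 160 | 5% | 0.142 | 0.569 | 0.854 | 0.961 |

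For example, with n = 88, q = 5% and f = 0.5, the 3-month count uses 0.05 × 0.5 = 0.025 and gives 18%; the 6-month count uses 0.05 and gives 65%.

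**4. Effect during recruitment.** Step 3 assumes that every patient has finished follow-up, which is not so while patients are still entering. Take 88 eTUSr patients entering uniformly over 24 months, q = 5% and onset linear over 6 months. At month 24 the mean time at risk is (21 × 3 + 3 × 1.5)/24 = 2.81 months for the 3-month count and (18 × 6 + 6 × 3)/24 = 5.25 months for the 6-month count. The expected numbers of cases are 88 × 0.05 × 2.81/6 = 2.06 and 88 × 0.05 × 5.25/6 = 3.85.

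| Trial month | P(≥ 4), 3-month count | P(≥ 4), 6-month count |
|---|---|---|
| 12 | 2% | 8% |
| 18 | 6–7% | 30% |
| 24 | 15% | 54% |

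**5. Whether the general stopping condition fills the gap.** It asks for a statistical as well as a clinical difference, and names no test. With 88 per arm, two-sided Fisher's exact test gives p = 0.059 for 5 stenoses against 0, and falls below 0.05 only at 6 v 0, 8 v 1 or 10 v 2. An uncorrected chi-squared test would be met at 4 v 0 (p = 0.043). Under the exact test this route therefore needs more eTUSr cases than the count of 4, and it needs a judgement that continuing is unethical.

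**The case against.** A reader might infer that a stenosis in months 4 to 6 can never lead to a review or a stop. The documents do not support that. The last stopping condition in section 8.4 has no time window, the committee assesses adverse events at each meeting, and the synopsis has complications reported to it. What is missing is a pre-specified count, not every route to action.

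A reader might also infer the same gap for urinary leak, whose case count covers the first month while the endpoint runs to 3 months. That does not hold either. Section 8.2 has any leak in either arm reported to the committee at once, without a time limit. The 1% leak limit can also be read without a window, and one leak in 88 patients (1.1%) would then meet it.

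Three further objections carry weight.

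- In section 8.4 and the synopsis, the words about 3 months may qualify only the count and leave the 20% limit open-ended. Section 8.2 points the other way, but as a description of risk. Since 20% means 18 cases in 88, this changes little in practice.
- An early-warning trigger shorter than the endpoint window can be a deliberate choice, and section 8.2 does speak of the early period. The protocol does not, however, say why the reason it gives for 6 months of recording should not apply to monitoring.
- A longer window on an unchanged count is not free. It has no comparator and no denominator, so it also fires more often when stenosis is rare. This stands and shapes the fix.

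**Conclusion.** The point holds as a gap in the pre-specified monitoring. The only stenosis case counts stop at 3 months, their time origin is not clear, and months 4 to 6 of the endpoint window are left to committee discretion. That the windows differ follows from the text alone. The size rests on assumptions that the protocol neither gives nor excludes: at a 5% six-month risk with half the cases early, the chance of reaching 4 cases in 88 patients is 18% against 65% with complete follow-up, and about 15% against 54% at the end of a uniform 24-month accrual with linear onset. If three quarters of cases appear by month 3, the 3-month figure rises to 42% and the loss is smaller; if a quarter do, it falls to 2.5%.

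**What to change.** Reconcile the synopsis and sections 8.2 and 8.4 with section 7.1 and the secondary endpoint:

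- In section 8.2, run the stenosis review count over each patient's 6-month endpoint window, and state that time is counted from that patient's transplant and not from trial start.
- Have the committee confirm, for that window, the numerical stopping limits in section 8.4 and the synopsis. The same count now leads to review in section 8.2 and to stopping in section 8.4; these passages must be reconciled too. No numerical limit is proposed here.

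The data are already collected to 6 months, so the direct cost is wording in three places. The real cost is more reviews, some of them false alarms. At assumed six-month risks of 2% to 3% with half the cases early, the chance of reaching 4 cases rises from about 1–4% to 10–27% with 88 patients, and from 8–22% to 40–71% with 160. For that reason the extended count should prompt a review, and the stopping limits should not be carried over to the longer window unexamined.

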#### 8.4.1 Direct Access to Source Data and Documents

The Investigator(s) will permit trial-related monitoring, audits, REC review, and regulatory inspections (where appropriate) by providing direct access to source data and other documents (i.e. patients' case sheets, X-ray reports, microbiology reports etc).

#### 8.4.2 Quality Assurance

Monitoring of this trial will be to ensure compliance with Good Clinical Practice and scientific integrity will be managed and oversight retained by the Joint Clinical Trials Office Quality Team.

# 9. PROJECT TIMESCALE

Our subject population appear to be motivated to be engaged and enrol in clinical research. In other studies in our unit over 75% of patients asked to participate in clinical research consent to be involved. We therefore believe that the required patient numbers on initial estimation (176) is achievable in 2 years given our transplant activity. If after our sample re-estimation the patient number required is higher (320), then we would need to recruit other centres to the trial. Other UK centres (such as Royal Free and Newcastle) have already expressed an interest to collaborate with us.

# 11. **DISSEMINATION AND OUTPUT**

It is intended that results will be published in peer reviewed medical journals and presented within the trust and at conferences externally. The results will be available to participants of the research study and transplant patients in the form of a leaflet if they wish. Results will also be sent to the local Kidney Patient's Association.

# 12. PUBLICATION POLICY

All data collected in this study is the intellectual property of the investigators

who should be included in the authorship of any presentation or publication of data as under international copyright laws.

# 13. APPENDICES

# A: Schematic diagram of the kidney transplant procedure and a ureteric stent.

#### **Transplantation Procedure Diagram:**

The donor kidney must be transplanted within 24-28 hours of removal from the donor. It is transplanted into the pelvic area and the donor kidney blood vessels are connected (anastomosed) to the recipient's blood vessels. The donor ureter is implanted into the bladder.

#### The Transplant Ureteric Stent:

This is placed in the transplant ureter with one end in the kidney and the other in the bladder. Diagram is approximately life size.

# **B:** Questionnaires to be used in the study

- Diary Cards for health economics assessment
- Quality of life validated questionnaires
  - FAIT-U (factit.org)
  - o EQ-5D (EuroQol)

# Children's diary card

| Participant study no.
DOB  |  |
|---|--|
| Initials
Sex   |  |
| 
 
Did you have to make an extra procedure?
 
                          | trip to the hospital for this                |
| - If yes, how did you travel here?  |  |
| - Did anyone come with you?   |  |
| - How much did this cost you/y  | our parents?                                 |
| - How long did it take?   |  |
| - Did you have to take time off's   | chool/ college to come today?                |
| - Did you parent(s) have to take  | time off work to come with you?              |
| 
 
Did you find it an inconvenien
anything important at school t
 
 | ce coming today? (E.g. did you mis
oday?) |
| 
 
How are you travelling home?
 
                                      |  |
| - How much will this cost you?  |  |
| 
 
How much time have you spen
today?
 
                            | it from your day on this procedure           |

Adult's diary card

|   | Patient ID   |
|---|--|
|   | F allent ID  |
|   | Participant Study No
DOB:   |
|   | Sex:   |
|   | Jex  |
|   |  |
| • | Day Of Stent Removal: (please insert date)20   |
|   | Did you have to make an additional trip to the hospital for this procedure?  |
|   |  |
|   | - If yes, how did you travel here?   |
|   | - How much did this cost you?  |
|   | - How long did it take?  |
|   | Did you find it an inconvenience attending the procedure today?  |
|   |  |
|   | Did you have to make any special arrangements to allow you to come to this   |
|   | appointment?
- Work:  |
|   | - Home#amily:  |
|   |  |
| • | Did you have to ask anyone to come with you?   |
|   | How are you travelling home?   |
| - | - How much will this cost you?   |
|   | - now many with this dost you:   |
|   | How much time have you spent from your day on this procedure today?
on the time you arrived for your appointment until the time you left) |

